**Principal Investigator is ultimately responsible for all aspects of the project including:**

A. It is the responsibility of the PI to ensure that each subject is adequately informed and freely consents to participate in the research. The PI will personally ensure that every reasonable

precaution is taken to reduce risks to the study participants, including subjects who are enrolled initially but prove to be screen failures or for whom data is incomplete, unusable, and/or otherwise eliminated during analysis.

B. It is the responsibility of the PI to delegate responsibility to the research staff in a manner that is commensurate with the staff's training and qualifications.

C. It is the responsibility of the PI to ensure that all procedures associated with the research are performed in accordance with the protocol, including the schedule of events as applicable, with the appropriate level of supervision, only by individuals who are licensed or otherwise qualified to perform them under the applicable laws, regulations, and policies.

D. The PI will ensure adherence to the study protocol and monitor the informed consent process.

E. The PI will ensure that there are appropriate facilities and resources to conduct the research.

F. It is the responsibility of the PI to be available to the research staff as needed and to regularly review research processes and address any deficiencies identified through quality improvement processes. The PI may also contact funding partners to schedule an external assessment of his or her research through an on-site visit and a regulatory audit of the protocol file. The PI is responsible for maintaining documentation of any quality improvement process for their specific studies.

G. It is the responsibility of the PI to ensure that adequate staff, resources, and professional practices and standards of care are maintained at external performance sites.

H. It is the responsibility of the PI to evaluate the intermediate and final results of the project and to take a leading role in the preparation of the final report.

## **5. LIST OF ABBREVIATIONS**

LDL- Low Density Lipoprotein

HDL- High Density Lipoprotein

VLDL- Very Low Density Lipoprotein

PI- Principal Investigator

CT- Computed Tomography

AST- Aspartate Aminotransferase

ALT- Alanine Aminotransferase

LDH- Lactate Dehydrogenase

NASH- Non Alcoholic Steatohepatitis

PTDC- Phosphatidylcholine

## **6. PROTOCOL SUMMARY**

***Full Title:* EFFECT OF LYCOSOMAL FORMULATION OF LYCOPENE CHAPERONED WITH PHOSPHATIDYLCHOLINE ON PROGRESSION AND OUTCOMES OF NONALCOHOLIC STEATOHEPATITIS**

**Short Title: EFFECT OF LYCOSOMAL FORMULATION OF LYCOPENE  
CHAPERONED WITH PHOSPHATIDYLCHOLINE ON NONALCOHOLIC  
STEATOHEPATITIS**

**Sample Size**

40 subjects divided into two clinical groups, 20 subjects in each group).

**Study Population**

Newly diagnosed and confirmed patients with NASH, males and females, aged from 40-65 years.

**Study Design**

The study is designed as a double-blinded, interventional, randomized clinical study involving patients with NASH. A major research question is whether ingestion of lycopene stabilized with Lycosome™ formulated phosphatidylcholine chaperone can reverse clinical and laboratory manifestations of NASH. Therefore, the primary endpoint of the project is the size of the liver and parameters reflecting lipid accumulation in the hepatic tissue at the end of the interventional period. Changes in the activity of liver-specific enzymes and parameters of lipid homeostasis represent the secondary question since normalization of serum levels of hepatic enzymes represents another important criterion of liver damage and its reversal in NASH. Biochemical parameters in serum specimens will be investigated before commencing the study, at the intermediate time points of 1 month and in the end of the study after 2 months treatment. To assess changed in the liver span Ultrasonography was used before and in the end of the trial.

Subjects will be assigned to take orally once a day either capsules containing 450 mg of regular phosphatidylcholine or 450 mg of the same phospholipid in Lycosome™ formulation with 7 mg of lycopene (Cambridge, UK).

The formulations will be dispensed to the subjects during follow-up visits each month. Monthly visits are planned to determine compliance and adherence to the protocol. A basic medical check-up will be performed and subjects will be asked questions to determine adherence to the protocol during each visit.

Packaging and labeling of the study products will be carried out according to the guidelines of NIH and US Department of Health and Human Services as recommended for biologics and investigational health food products. The formulations will be shipped to the study site in specially designed containers with primary and secondary components. The container closure system will prevent exposure of the investigational products to light, moisture, temperature extremes and air. This packaging system guarantees stability of the product for intended use. Protection from microbial contamination will be provided by maintaining container integrity after the packaging system is sealed. An adequate and validated procedure was used for investigational product manufacture and packaging.

All individual packages will be labeled with a numerical code. None of the volunteers or trial personnel will be informed of study group assignment for the duration of the study. Unblinding of the results is planned to be performed by an independent statistician who will be hired and assigned to the work at the end of the study period.

Upon arrival at the clinical site the study products will be inspected by the Medical Officer and Clinical Monitor, then placed in a locked room at the clinic. Only the Medical Officer, PI and Clinical Monitor will have access to the products during the study period. Each subject will be given a one month supply of the study product at the "zero" time point of the study and then subsequently for each month of the study period following verification of compliance with the study protocol.

Total study duration is six months with a medical check-up for each volunteer at the "0" time point of the study as well as at 1st month and at the 2nd, the end of the interventional period.

During the medical check-ups each volunteer will be subjected to thorough clinical and laboratory investigation. Clinical investigation will include reading the vital signs, determination of body mass index, anthropometry, blood pressure measurement and computed tomography (at the initial and final time points of the study). Among laboratory tests will be determination of fasting serum glucose and lipids (total cholesterol, LDL, HDL and total triglyceride

[figure not shown]

levels), determination of ALT and AST levels, alkaline phosphatase, gamma glutamyl transpeptidase, lactate dehydrogenase, total bilirubin, CRP, LDL oxidation and IOD. Moreover, serum lycopene concentration and lycopene isomer profile will be measured at the initial and final points of the interventional period. All volunteers will also be subject to a standard hematological investigation.

Results collected for each volunteer will be stored as both paper files and digital files in Excel format and will be available for access by the Medical Officer, Medical Monitor and PI. To avoid any bias each subject will be given a random computer code containing three numerical characters and three letters. Decoding of the individual results will be carried out by an independent statistician hired for the purpose.

Packages containing the study formulations will be coded and blinded for both the subjects and medical personnel conducting the study. Only the Principal Investigator will be informed of package contents and the subjects belonging to each study group.

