### **7.3 Clinical Study Objectives**

### **7.3.1 Primary objective**

The primary objective of this clinical study is to verify the effect of a novel formulation of lycopene fused with phosphatidylcholine chaperone on liver size and function as well as progression and outcomes of nonalcoholic steatohepatitis (NASH).

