#### **Secondary objectives**

- Investigation of the effect of a novel formulation of lycopene fused with phosphatidylcholine chaperone on tomographic parameters of liver in NASH patients.
- Evaluation of the effect of a novel formulation of lycopene fused with phosphatidylcholine chaperone on liver specific enzymes including alanine aminotransferase, aspartate aminotransferase, gamma glutamyl transpeptidase, alkaline phosphatase and some others in NASH patients.
- Assessment of the effect of phosphatidylcholine chaperone alone on tomographic parameters of liver and plasma biochemistry values in NASH patients.

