## **11. SAFETY AND EFFECTIVENESS ASSESSMENTS**

Safety assessment procedures are barely applicable to the current study since widely consumed food ingredients will be used for the study. Volunteers with intolerance or adverse reaction to phospholipids or lycopene will not be enrolled in the study.

Effectiveness assessment will be performed by measuring liver size and serum lipid levels at the intermediate and final points of the interventional period.

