## **13. STATISTICAL METHODS/DATA ANALYSIS**

### **13.1 Study endpoint**

For assessment of normally distributed parameters the Shapiro-Wilk method will be used. Student's t-test will then be applied for both paired and unpaired samples. Between-group differences at one time point will be evaluated by Wilcoxon-Mann-Whitney test (continuous variables) and Fisher's Exact test (categorical variables). Data analysis will be performed using Stata SE, version 12.1. All statistical tests will be two-sided and statistical significance level alpha will be set at 0.05 for the analysis.

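### The primary variable, its imaging method and its time point are stated inconsistently, so the protocol does not fix one test of success

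*Protocol*

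**What the plan says.** **Primary variable**

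- Section 6, Study Design: "the primary endpoint of the project is the size of the liver and parameters reflecting lipid accumulation in the hepatic tissue", assessed at the end of the interventional period. The same paragraph makes liver enzymes and lipid homeostasis the secondary question.
- Section 7.3.1: the primary objective is the effect of the formulation "on liver size and function as well as progression and outcomes of nonalcoholic steatohepatitis (NASH"). Lipid accumulation is not mentioned.
- Secondary objectives under 7.3: these include the effect "on tomographic parameters of liver in NASH patients" and the effect on liver enzymes.
- Section 11: effectiveness is assessed by "measuring liver size and serum lipid levels at the intermediate and final points of the interventional period".
- Section 11.2: CT, blood pressure, liver enzymes and four serum lipids are listed without ranking.

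**Imaging method**

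- Section 6, Study Design: "To assess changed in the liver span Ultrasonography was used before and in the end of the trial". Later in the same section, the check-ups include "computed tomography (at the initial and final time points of the study").
- Section 7.4.2 schedules CT at day 0 and at the last visit. It does not schedule ultrasonography.

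**Time point**

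- Section 6 places the end of treatment at month 2, although it also gives a total study duration of six months.
- Sections 7.4.2, 7.4.3 and 7.4.6 run the intervention to month 6.

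**Tests and power**

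- Section 13.1 is headed as the study endpoint but names none. It lists paired and unpaired t-tests and the Wilcoxon-Mann-Whitney test, then states: "All statistical tests will be two-sided and statistical significance level alpha will be set at 0.05 for the analysis".
- Section 13.2 claims 90% power at one-sided 2.5% with 40 per group. It gives no endpoint, difference or standard deviation.

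**The concern.** A trial has one clear test of success when the protocol fixes what is measured, how, when, and by which comparison. Here each of these has either more than one answer or none. An analysis plan written from this protocol would have to choose which section to contradict.

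Two things are at stake. The first is the error rate. With more than one primary measure, every test at 0.05 and no rule for combining them, success could be claimed on whichever measure or imaging method gives the favourable result. The second is power. A 90% power statement means something only for a named variable with a stated difference and spread, and 13.2 supplies none of these.

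**Working it through.** **1. Sections side by side**

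| Item | Section 6 | 7.3.1 and secondary objectives | 7.4 | 11 and 11.2 |
|---|---|---|---|---|
| Liver size | primary | primary | – | effectiveness measure |
| Lipid accumulation in liver | primary, parameters unnamed | not named | – | not named |
| Function, enzymes | secondary | function primary, enzymes secondary | – | enzymes listed, unranked |
| Progression and outcomes | not named | primary, no measure given | – | not named |
| Tomographic parameters | – | secondary | – | CT listed, unranked |
| Serum lipids | secondary | – | – | effectiveness measure |
| Imaging | ultrasonography for span; CT at start and end | tomographic | CT only (7.4.2) | CT only |
| End of intervention | month 2 | – | month 6 | – |

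Liver size is the only variable shared by the section 6 endpoint, the 7.3.1 objective and the section 11 assessment. Section 11 wants it at intermediate points as well. The intermediate visits in 7.4.2 (months 2 and 4) are physical and laboratory only, and section 6 places both imaging methods at the start and end only. No imaging is therefore scheduled that could supply an intermediate liver size.

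**2. The plan's own sample size**

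The figure of 80 cannot be reproduced, because 13.2 gives no difference, standard deviation (SD) or endpoint. Only the standardised difference can be back-solved. One-sided 2.5% and two-sided 5% share the critical value 1.960, so they do not conflict on this point. By normal approximation with equal arms:

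d = (1.960 + 1.282) × √(2/n)

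- n = 40 per group (13.2): d = 3.242 × 0.2236 = 0.725 SD.
- n = 20 per group (section 6, Sample Size): d = 3.242 × 0.3162 = 1.025 SD.

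Neither value can be set against a clinical difference, since none is attached to any variable.

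**3. If any one primary measure may win at 0.05**

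For k independent measures, the chance of at least one false positive is 1 − 0.95^k. The correlated figures come from simulating 2,000,000 sets of normal test statistics with equal correlation. The number of measures and the correlation are assumptions.

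| Measures | Independent | Correlation 0.5 | Correlation 0.9 |
|---|---|---|---|
| 2 | 1 − 0.95² = 9.75% | 9.1% | 7.0% |
| 3 | 1 − 0.95³ = 14.3% | 12.6% | 8.4% |

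The two-measure row treats lipid accumulation as one variable. The protocol uses the plural, so three or more is possible.

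**4. If all primary measures must succeed**

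The false-positive rate stays at or below 5%. With two measures, each at 90% power and independent, joint power is 0.90 × 0.90 = 81%. It is higher if they are positively correlated, up to 90%.

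**5. Keeping two primary measures with alpha split**

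At 0.025 each, the critical value is 2.241.

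- Power at 0.725 SD with 40 per group: Φ(3.242 − 2.241) = Φ(1.00) = 84%.
- n per group for 90%: 2 × (2.241 + 1.282)² / 0.725² ≈ 47.2, so 48.

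**The case against.** Four points can fairly be made on the other side.

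- Only section 6 uses the term primary endpoint. Section 7.3.1 states an objective, and section 11 lists assessments without calling them primary. A reader might infer three rival primary endpoints, but the text does not support that. What stands is the conflict between the section 6 endpoint and the 7.3 objectives, and the unmatched visit timing in section 11.
- Multiplicity is commonly handled in a statistical analysis plan, which is not at hand. A missing adjustment is therefore no finding, and a two-sided 0.05 level is not wrong in itself. What stands is that the protocol states its primary variable inconsistently and ties no test to it.
- A reader might count about twelve effectiveness parameters in 11.2 and quote 1 − 0.95^12 = 46%. That ignores a ranking the protocol does give: section 6 makes enzymes and lipid homeostasis secondary, and nothing makes blood pressure primary. It also assumes independence among related laboratory values. The figure should not be used.
- A reader might infer that ultrasound and CT will be mixed within one change score, adding method error. Section 6 plans each method at both start and end, so no mixed change is planned. Ultrasound span could even be the primary measure with CT parameters secondary, which would fit the secondary objectives. But no sentence says so, and 7.4.2 schedules no ultrasound.

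**Conclusion.** The concern holds in this form: the primary variable, the imaging method that supplies it and the time at which it is read are each stated inconsistently, and no test is tied to a primary variable. The 90% power in 13.2 therefore belongs to no endpoint.

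The effect on the error rate is conditional. It is up to 9.75% if there are exactly two primary measures and either may win, and about 9.1% or 7.0% at correlations of 0.5 or 0.9. If both must succeed, there is no inflation and the cost falls on power (81% under independence, if each measure had 90%). The wording of section 6 joins the two parts but does not say which rule applies, so neither error rate is fixed by the document.

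The contradictions between sections rest on the text alone. The sizes rest on the assumed number of measures, their correlation and the normal approximation.

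**What to change.** - In section 6 (Study Design), 7.3.1, 11 and 13.1, name the same single primary variable. Liver size is the natural candidate because section 6, 7.3.1 and 11 all contain it.
- State one imaging method for it, used at baseline and at the end of intervention in every subject. Make 7.4.2, 11.2 and the tomographic objectives agree with that method. Leave the CT wording in the inclusion criteria (Study Schema and 7.4.4) as it is, since that concerns diagnosis.
- In 13.1, name one between-arm test for that variable at two-sided 0.05, and state in 13.2 that the power refers to it.
- Make lipid-accumulation parameters, enzymes and serum lipids secondary and supportive.
- In section 11, remove the intermediate points for liver size.
- Reconcile section 6 (month 2) with 7.4.2, 7.4.3 and 7.4.6 (month 6), so that the endpoint has one time point. Which period is right is for the sponsor to settle.

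The cost is protocol wording, and the other measures lose confirmatory status. If the sponsor prefers to keep lipid accumulation as a second primary measure, the protocol must name it and say whether one or both must succeed. Under an either-may-win rule with 0.025 each, power at 0.725 SD falls to 84% with 40 per group, and 48 per group restores 90%.

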## **7.4 Study Design**

### **7.4.1 Selection and randomization of volunteers**

Medical personnel from the outpatient clinic of the Institute of Cardiology, Saratov, Russian Federation will be informed about launching the study, its major goal and selection criteria for volunteers. Suitable individuals will be invited for a preliminary check-up (physical and laboratory investigation) during the initial phase of enrolment. All suitable individuals will be re-screened after the wash-out period of the study before the final decision on study enrolment is made.

Randomization of volunteers in the study will be performed using widely accepted methods such as simple randomization and stratified randomization. Briefly, software containing a random number generator will be applied to the database of volunteers. The assigned group will be considered final. The groups will be balanced according to numerical age and gender with special software.

Stratified randomization will be used to enhance the statistical power of the final results and will ensure equality of groups for secondary selection criteria.

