### **8. STUDY DRUG STORAGE AND ACCOUNTABILITY**

The Principal Investigator and Medical Officer for the study are responsible for ordering, receiving, and tracking inventory; storing, dispensing, and returning study products properly; and, where necessary, labeling of study products prior to dispensing according

to protocol guidelines and good manufacturing practices (GMPs). All study products supplied for the protocol will be accounted for and tracked in a manual or electronic accountability log for the study. Accountability for the study products will be documented from the time of initial receipt through dispensation and final disposal of leftover study products. The accountability log will indicate the date, amounts, batch numbers, and condition upon receipt of all materials received from the supplier. Upon study completion remaining study products will be returned or destroyed as defined by specific Investigator instructions, or other documented instructions. The balance returned or sent for destruction will be recorded in the study accountability log. Quality assurance reviews and inspections of study product accountability documentation will be performed at intervals during the study by the Clinical Monitor. Study products will be stored at the clinical site facility in a locked cabinet.

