### **13.3 Statistical effectiveness analysis**

Statistical analysis of results will be performed by an independent statistician. If the statistical methods and settings listed above are not appropriate for the newly obtained results due to specificity of variant distribution, other methods of statistical analysis will be applied. Any deviations from the statistical plan described above will be explained and justified in a protocol amendment and/or in the final report submitted to the Institutional Ethics Committee.

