## **17. STUDY DISCONTINUATION CRITERIA**

### **17.1 Discontinuation of individual research subjects**

Individual research subjects can be withdrawn from the study due to occurrence of adverse effects, volunteer's request (regardless of reason) and non-compliance with the protocol. Volunteers withdrawn from the study will be replaced from the pre-screened pool of volunteers.

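### Allocation of replacement subjects is not protected from foreknowledge: the Principal Investigator is said to know the arms, no rule assigns replacements, and the only named independent party arrives at the end

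*Protocol*

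**What the plan says.** **Independent party.** Section 6 (Study Design) leaves unblinding to "an independent statistician who will be hired and assigned to the work at the end of the study period". It adds: "Decoding of the individual results will be carried out by an independent statistician hired for the purpose". Section 13.3 gives the remaining task: "Statistical analysis of results will be performed by an independent statistician". No task is placed before or during allocation.

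**Who knows the arms.** Section 6 first says: "None of the volunteers or trial personnel will be informed of study group assignment for the duration of the study". The last paragraph of the same Study Design text says that packages are blinded to subjects and medical personnel, but that the Principal Investigator, alone, will know what the packages contain and which subjects are in which group.

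**Making and keeping the list.** Section 7.4.1 says that "software containing a random number generator will be applied to the database of volunteers", and that the resulting group is final. It names no operator. Section 15.2 lists the master randomization list and the decoding procedures among the records that the Sponsor-Investigator maintains. Section 8 makes the Principal Investigator and Medical Officer responsible for "storing, dispensing, and returning study products properly; and, where necessary, labeling of study products prior to dispensing".

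**Replacement.** Section 17.1: "Volunteers withdrawn from the study will be replaced from the pre-screened pool of volunteers". Section 12.2 says the same for withdrawals after an adverse reaction or abnormal laboratory finding. Neither section says who chooses the replacement, in what order the pool is used, or how the arm is set.

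**The concern.** This is about concealment before a subject is assigned, which coded packages do not provide. A replacement is chosen from people who have already been examined and whose laboratory results are on file. If the person choosing knows which arm the place belongs to, a volunteer with a better outlook can be taken for one arm and passed over for the other, knowingly or not. The between-group tests in Section 13.1 would count that difference as a treatment effect and could not detect it.

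Replacement could be a regular route of entry. The stated triggers are poor adherence (Section 9), any adverse reaction or abnormal laboratory finding (Section 12.2) and the volunteer's own request (Section 17.1), in a population enrolled partly on its laboratory results.

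**Working it through.** The protocol gives no figure on this point to reproduce, so the main check is a comparison of its statements.

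**Step 1. Does anyone who could influence entry know the arms?** Section 6 answers both no (all trial personnel) and yes (the Principal Investigator). Because the two statements conflict, concealment cannot be taken from the first. Section 15.2 is consistent with the second, since it places the list among the Sponsor-Investigator's records.

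**Step 2. Could the independent statistician prevent this?** No. That person's tasks are unblinding, decoding and analysis, and the engagement starts at the end of the study. The hiring date does not itself create foreknowledge. It means that the one independent person named cannot hold the list while subjects are entering.

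**Step 3. How might a replacement get an arm?** The text allows four readings:

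| Reading | Can a person who holds the list foresee the arm? |
|---|---|
| Replacement inherits the vacated place | Yes |
| Replacement takes the next entry on a prepared list | Yes |
| The whole pool was randomised in advance | Yes |
| Replacement is freshly randomised after being chosen | No |

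Three of the four are exposed if the Principal Investigator knows group membership, and the protocol does not select the fourth.

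**Step 4. Is the initial cohort exposed?** Section 7.4.1 re-screens candidates before the final enrolment decision and then applies software to a database. If that is one batch of people already selected, there is no next arm to foresee. The exposure is therefore clearest for replacements.

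**Step 5. Illustration of size.** Known inputs: one-sided 2.5% (Section 13.2, the same upper tail as the two-sided 0.05 in Section 13.1), and 20 per group (Section 6) or 40 per group (Section 13.2). Assumed inputs, none of them in the documents:

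- a fraction f of test-arm places is filled by the better of two candidates;
- r is the correlation between the chooser's judgement and the outcome.

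The expected larger of two standard normal values is 1/√π = 0.564. Bias in SD units = f × 0.564 × r. Error = upper tail of the noncentral t beyond t(0.975, 2n−2), with noncentrality = bias/√(2/n). Example: f = 0.20, r = 1, n = 40 gives bias 0.113, noncentrality 0.113/0.2236 = 0.505, and error 7.19%.

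| f | r | Bias (SD) | Error, 40 per group | Error, 20 per group |
|---|---|---|---|---|
| 10% | 1 | 0.056 | 4.36% | 3.70% |
| 20% | 1 | 0.113 | 7.19% | 5.35% |
| 10% | 0.5 | 0.028 | 3.32% | 3.05% |
| 20% | 0.5 | 0.056 | 4.36% | 3.70% |

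If the worse of two is also taken for control at f = 20%, the bias doubles. At r = 1 it is 0.226 SD, with error 16.8% at 40 per group and 10.3% at 20. At r = 0.5 it is 0.113 SD, with error 7.2% and 5.4%.

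**The case against.** A reader might infer that no independent person exists to make the list, and so that the study team generates it. The documents do not support that. Section 7.4.1 is in the passive and names no operator, the late hire is tied to unblinding, decoding and analysis, and part of Section 4 (Key Roles) was not in the text available for this review. What can be said is that the available text names no other independent party.

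A reader might also infer that arms can be foreseen whenever any subject is chosen. That does not follow either. It would need someone informed of the allocation, and the only such person described is the Principal Investigator, in a statement that the same section contradicts. The Medical Officer, who withdraws subjects, is among the personnel described as blinded. Batch randomisation of the initial cohort is a natural reading of Section 7.4.1.

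Three further objections have force:

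- Section 8 provides for labelling only where necessary, and Section 15.2 is a record-keeping list. Neither proves who holds the list during enrolment.
- The error rates rest on an assumed rate and an assumed quality of judgement, so they cannot carry the argument.
- Section 13.1 already fixes the tests and alpha, Section 13.3 requires deviations to be justified, and an analysis plan may exist. The timing of the hire is therefore not, on its own, a fault in the analysis.

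What remains is the contradiction over who knows the arms, the absence of an assignment rule for replacements, and an independent party whose start date is fixed too late to help.

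**Conclusion.** The point holds for replacement subjects. The protocol says in one place that the Principal Investigator knows group membership, makes the list a Sponsor-Investigator record, and refills withdrawn places from characterised volunteers with no concealed assignment rule. It is not established for the initial cohort, and it does not show that anyone would misuse the knowledge.

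The size of the bias cannot be estimated from the documents, because they give no replacement rate and no measure of how well a chooser could predict outcome. The figures above only show that modest steering could matter. With steering towards the test arm alone they run from 3.05% to 7.19% against a nominal 2.5%, and the upper end needs perfect prognostic judgement. The matter should be settled before the first subject is randomised. It is a question of trial conduct that an analysis plan cannot repair afterwards.

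**What to change.** 1. **Section 6 (Study Design) and Section 7.4.1:** engage the independent statistician before the first randomisation. That person generates the list and the package numbering and holds the code, until the data are locked, away from everyone who screens, enrols or assesses subjects, including the Principal Investigator.
2. **Section 6:** reconcile the two statements on who knows group assignment, so that one rule remains.
3. **Sections 12.2 and 17.1:** state that any later entrant takes the next unused number in the concealed sequence, after eligibility has been signed off.
4. **Section 13.3:** require the primary analysis to be fixed in writing before decoding. Because the same person would hold the code and do the analysis, a dated version that precedes the list would be the safer record.

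The cost is an amendment to a few paragraphs and an earlier, somewhat longer engagement of a statistician the protocol already plans to hire. The documents show no budget, so that cost cannot be priced here.
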